5.5.2. Dose Modifications for Bicalutamide

Not allowed. In case of CTCAE grade 3 or 4 transaminase elevation, bicalutamide will be stopped until the event resolved to Grade 1 or less.

5.6 Duration of Therapy

In the absence of treatment delays due to adverse events, treatment may continue for 8 cycles (32 weeks) or until one of the following criteria applies:

- Disease progression
- Intercurrent illness that prevents further administration of treatment,
- Unacceptable adverse event(s)
- Patient decides to withdraw from the study
- General or specific changes in the patient's condition render the patient unacceptable for further treatment in the judgment of the investigator.

5.7 Medication Compliance

At each study visit, patients should be instructed on the proper dosing regimen. Any missed doses should be documented in the patient's study record. Patient should be instructed not to make up any missed doses.

5.8 Concomitant Medications and Treatments

All concomitant medications received within 28 days before the first dose of study medication and 30 days after the last dose of study medication will be recorded in the patient study records, including all prescription, over-the-counter, herbal supplements, and intravenous medications and fluids. Any changes to the concomitant medication regimes should be recorded throughout the study.

5.9 Duration of Follow-up

All patients will be followed for response during 32 weeks, and followed for survival, adverse events, and disease status every 12 months (+/- 2 months) for up to 5 years from end of treatment. Any patients who experience adverse events should be followed until one of the following occurs:

Resolution of the adverse event to \leq Grade 1 or baseline severity.

Determination that the adverse event is stable and will not resolve.

Initiation of another anti-cancer treatment.

6.1 STUDY PROCEDURES

6.1 Schedule of Assessments

A Cycle is defined as 4 weeks. Patients will be evaluated according to the schedule in Table 1.

Table 1. Schedule of assessments

Assessment	Screening ¹	Treatment cycles ²									Off Treatment ⁷	Follow Up ⁹
		Cycle 1	Cycle 2	Cycle 3	Cycle 4	Cycle 5	Cycle 6	Cycle 7	Cycle 8			
Informed consent	X											
Tissue collection consent	X											
Demographics	X											
Medical history	X											
Concomitant Medications	X		X	X	X	X	X	X	X	X	X	
Review of Systems	X		X	X	X	X	X	X	X	X	X	
Physical exam ²	X		X	X	X	X	X	X	X	X	X	
Vital signs ³	X		X	X	X	X	X	X	X	X	X	
Adverse event recording			X	X	X	X	X	X	X	X	X	X
Height	X											
Weight	X	X	X	X	X	X	X	X	X	X	X	
ECOG PS	X		X	X	X	X	X	X	X	X	X	
CBC with differential ⁶	X			X							X	
Serum Chemistry ^{4,6}	X		X	X	X	X	X	X	X	X	X	
Fasting Lipids ^{5,6}	X			X							X	
PSA ⁶	X	X	X	X	X	X	X	X	X	X	X	
Testosterone ⁶	X	X	X	X	X	X	X	X	X	X	X	
HgbA1c	X			X							X	
Vitamin B12	X										X	
CT CAP with IV contrast ⁸	X											
Bone scan*	X											
Research blood	X			X							X	
Research blood, optional	X			X							X	
FACT – P, version 4	X										X	
Survival & disease status ⁹												X

1. Physical examinations, blood tests must be performed within 2 weeks of treatment.
2. Evaluation is scheduled Day 1 of each cycle +/- 2 days to allow for logistical issues.
3. Vital signs include temperature, pulse, respiratory rate, and blood pressure
4. Albumin, alkaline phosphatase, total bilirubin, bicarbonate, BUN, calcium, chloride, creatinine, glucose, potassium, phosphorous, magnesium, total protein, SGOT, SGPT, sodium

15-1015

5. Cholesterol, LDL, HDL, Triglycerides.
6. All Labs (CBC, chemistries, fasting lipids, PSA, and testosterone) may be drawn up to 3 days prior to day 1 if site is unable to obtain results on day of treatment.
7. Off treatment evaluation should be scheduled at week 33 +/- 2 days to allow for logistical issues.
8. At physician discretion, a Chest x-ray can be done in place of a Chest CT at screening. Repeated bone or CT scans can be ordered during treatment if clinically indicated.
9. Follow up by telephone will occur once annually for 5 years, starting a year after the off-treatment visit +/- 2 months.

6.2 Screening

All patients must undergo pre-treatment evaluations. Pre-treatment evaluations will be used to determine the patient's study eligibility and will include a history and physical (including height and weight), ECOG performance status score, vital sign measurements, CBC with differential and platelet counts, and serum chemistry profiles. Imaging studies for baseline tumor assessment will be performed within 6 weeks of the initiation of therapy. Patients must sign an informed consent form prior to undergoing protocol-specific evaluations (prior imaging studies are allowed in order to decrease radiation exposure) and receiving treatment. Patients may be re-screened if they previously failed the pre-treatment evaluation. Rescreening must occur 3 months or more from last screening and a maximum of 2 re-screenings are allowed.

6.3 Treatment Evaluations

Patients will be examined by the treating physician or designee on day 1 of each cycle prior to treatment. This examination will include a physical exam, toxicity assessment, concomitant medication review, and performance status. The physical exam must not occur more than 14 days prior to day 1 treatment. Chemistries, PSA, testosterone will be performed every 4 weeks, prior to each cycle. All required labs (such as CBC, chemistries, lipids, PSA, testosterone, etc) may be drawn up to 3 days prior to day 1 if site is unable to obtain results on day of treatment.

6.4 End of Study and Follow up

Patients will have an evaluation and physical examination when they are taken off study treatment or complete study treatment (week 33). The reason for ending study treatment must be described in the source document and in OnCore. This evaluation will include a physical examination (including weight and vital signs), ECOG performance status score, CBC with differential and platelet counts, serum chemistry profiles, PSA, testosterone, HgbA1c, fasting lipids, research blood collection and toxicity assessment. Patients will be contacted every 12 months (+/- 2 months) to collect survival information, disease status, and the presence of persistent AEs for the next 5 years.

7.0 MEASUREMENT OF EFFECT

7.1 Definitions of Biochemical Response and Progression

7.1.1 Complete Response: PSA <0.2 ng/mL confirmed on two consecutive

26

additional determinations taken at least 4 weeks apart.

7.1.2 *Partial Response:* A reduction in PSA $\geq 50\%$ from baseline without evidence of clinical or radiographic progression confirmed on two consecutive additional determinations taken at least 4 weeks apart.

7.1.3 *Stable Disease:* Patients who do not meet the criteria for response (CR or PR) or serological progression for at least 3 months (90 days) will be categorized as having stable disease.

7.1.4 *Progressive Disease:*

1) For patient who achieved a $\geq 50\%$ decline in PSA, progression is defined as an increase in PSA value by 50% above baseline or nadir (whichever is lowest), confirmed by a second PSA rise at least two weeks later. The PSA rise must be at least 5 ng/mL. Changes in PSA below 5 ng/mL will not be considered assessable for progression.

2) For patients with an undetectable PSA nadir (< 0.2 ng/mL), progression is defined as a PSA rise to the detectable range (detectable PSA is ≥ 0.2 ng/mL) confirmed by a second PSA rise at least 2 weeks later.

3) For patients whose PSA has not decreased by 50%, progression is defined as an increase in PSA value $\geq 50\%$ of baseline (on trial) or nadir PSA, whichever is lowest, confirmed by a repeat PSA at least 2 weeks later. The PSA must have risen by at least 5 ng/mL.

7.2 Radiographic Progression

The appearance of new lesions on examination or radiographs (CXR, CT scan, MRI scan, or bone scan) with or without a concurrent increase in serum PSA from baseline.

7.3 Survival

Survival will be measured from the date of randomization.

7.4 Time to PSA Progression

Time to PSA progression is defined as time from randomization to first confirmed rise in PSA (or development of clinical progression) meeting progressive criteria after starting bicalutamide treatment.

7.5 Time to PSA Nadir

Time to PSA nadir is defined as the time from randomization to the date that PSA nadir is documented. PSA nadir is defined as the lowest PSA value achieved after registration or baseline PSA, whichever is lowest.

7.6 PSA Slope

The change in PSA will be graphically depicted and a PSA slope calculated. The change in PSA slope (and PSADT) pre-study, during-study, and off-study will be determined to see if the treatments have any disease modifying effects, especially in those patients experiencing stable disease. This end-point is exploratory, but may help to interpret PSA response.

7.7 Symptomatic Deterioration

Patients with a global deterioration of health status requiring discontinuation of treatment without objective evidence of disease progression at that time should be classified as having symptomatic deterioration.

7.8 Duration of Response

The period measured from the time that PSA criteria are met for complete or partial response (whichever status is recorded first) until the first date that progressive disease is documented.

7.9 Quality of life (QOL)

Quality of life will be assessed during the screening visit and after the study completion using The Functional Assessment of Cancer Therapy-Prostate (FACT-P) questionnaire. It is a relevant, worldwide tool used for assessing the health-related quality of life in men with prostate cancer.

8.0 TISSUE COLLECTION AND CORRELATIVE STUDIES

8.1 Pathology Review

There will be no central pathology review for this study. Patient must have diagnosis of prostate cancer histologically confirmed at the participating institution.

8.2 Tissue Collection

The collection of a representative block of the diagnostic tumor tissue (if available) is an important part of this trial; however, the participation of subjects is optional. Blocks will be carefully banked as part of the Fox Chase tissue/tumor bank. Tumor blocks will be the preferred material to collect, as one of the objectives will be to create tissue micro arrays. These will optimize the amount of tissue available to investigators and permit the preservation of the tumor block submitted. If, at any time, the submitting hospital requires the block to be returned for medical or legal concerns, it will be returned by

courier on request.

The tissue may be used by researchers now or in the future to better understand the nature of prostate cancer and how patients respond to treatment. Samples will be used for research purposes only and will not be sold. Patients will not be identified by name. The only identification of tissue will be by a patient study number assigned at the time of randomization to the trial the surgical/histology number and/or patient initials. Material issued to researchers will be anonymized and only identified by a coded number. Diagnostic pathology reports are received as part of the supporting documentation required for this trial. Testing for hereditary genetic defects predisposing to malignant disease will not be carried out without the expressed consent of the subject. All subjects on whom a diagnostic tumor block is collected will be aware of this retrieval and will have given their consent.

8.2.1 Use of Tumor Blocks

As part of the embedded correlative science for the protocol, the following research is planned using archival tissue samples collected and banked at the time of study entry:

a) Insulin Receptor (IR)

We plan to quantify IR expression by IHC and correlate results with clinical outcomes.

b) LKB1

We plan to quantify LKB1 expression by IHC and correlate results with clinical outcomes. LKB1 expression is key to the ability of metformin to affect AMPK activity within tumors and to suppress the growth-promoting outputs of this signaling pathway (i.e. mTOR-regulated protein translation). LKB1 expression is essential for direct (insulin independent) effects of metformin.

c) Phosphoantibody Markers of Activation of Key Signaling Pathways

Expression of IR and LKB1 will be indicative of the capacity of tumor cells to respond to indirect (insulin and IR mediated) and direct (insulin independent, LKB1 mediated) effects of metformin respectively, however, the expression of these factors cannot distinguish whether the pathways underlying these responses are actually activated. Multiple other genetic factors may alter pathway activation. As a result, activation markers of these pathways [PI3K (STMN1), PKB/Akt (P-PKB/Akt,) mTOR (P-4E-BP1) and IRS-1 (P-IRS-1)] will be evaluated as predictors of metformin benefit. If one or more of these biomarkers are activated at prostate cancer diagnosis, it is predicted that metformin benefit is possible. If none of these pathways is activated, it is predicted that metformin benefit will not be seen, regardless of IR and/or

LKB1 expression.

8.3 Use of Blood Samples

Correlative studies will be an integrated component of the clinical trial. Investigations of fasting glucose and insulin levels at baseline, 9 weeks post randomization and at the end of study treatment will be mandatory and will explore the indirect insulin-mediated effect of metformin on protocol defined outcomes. Other measurement will include, but not limited to IGF1 level Inhibition of the downstream targets of the mTOR pathway: 4E-BPI and p70S6K1, IGF-1/IGFBP-3 (observed on peripheral blood mononuclear cells (PBMCs)).

- a) Genomic/Gene Expression Profile Predictive of Metformin Benefit** Large-scale genomic studies over the past two decades have identified numerous recurrent genetic events in prostate cancer. More recent studies are focusing on building a comprehensive, genome-wide understanding of various types of prostate cancer. We plan to use such analyses to search for a genomic/gene expression profile predictive of metformin benefit. In the case of observed metformin benefit, we will perform comprehensive genomic/gene expression analysis of peripheral blood and available tumor material. Considering rapid technical advances in the genomic analysis arena, at the time of analysis, we will choose the most appropriate methodology to delineate the genetic/gene expression predictors of metformin benefit.
- b) Blood Collection and Analysis** Investigation of a core group of blood variables (at baseline, 9 weeks after enrolment and at the end of treatment) and tumor related factors (at diagnosis) will be examined as predictors of metformin benefit in this trial is outlined below. We will also collect additional samples that will allow us to examine a broader array of both prognostic and predictive factors in future work. The blood collection for fasting glucose and insulin is a mandatory part of the baseline, 9 weeks and end of treatment measurements.

After an overnight fast of at least 12 hours, participants will provide the following blood specimens: 1 tube for immediate glucose analysis (performed according to established institutional practice), light green topped tubes (containing lithium heparin - for plasma), red topped tubes (for serum) and lavender topped tube (for DNA). *Lavender topped tubes for DNA should be collected even for patients who consent to blood banking but refuse genetic testing. DNA may be used to study gene expression without fitting the definition of genetic testing.* The green topped tubes will be centrifuged within half an hour of collection and the plasma collected frozen immediately in 1 ml aliquots at -80°C. The red topped tubes will sit for 30 minutes at room temperature and then be centrifuged and the collected serum frozen immediately in 1 ml aliquots at -80°C. Lavender topped tubes (whole blood in EDTA) will be collected and frozen at -80°C in 1 ml aliquots for subsequent thawing and DNA extraction. Specimens will be stored at

participating centers immediately after collection and then shipped to a central laboratory, frozen on dry ice, in batches of 10 sets or more (1 set = entire blood collection at one patient visit), for subsequent storage and ultimate analysis. Our plan to collect lymphocytes for DNA at both baseline and at the end of study (week 33) will provide the necessary sample to evaluate not only germline DNA but also potential changes in DNA methylation as a result of the metformin intervention.

In addition to blood samples collection listed above additional blood samples will be collected at the NCI site for immune assessments in some patients (exploratory): 6 (10mL) green top sodium heparin tubes for PBMC and 2 (8mL) SST tubes for serum samples) at baseline, week 9 and week 32 (end of study). Immune assessments will be performed at the Laboratory of Tumor Immunology and Biology at the NCI's Center for Cancer Research (CCR) and will include flow cytometry-based and serum assays. Samples will be analyzed in batches after enrolling all patients in order to ensure best laboratory practices and quality data. From samples acquired the following assays will be performed:

- 1 Analyses of PBMCs: PBMCs separated by Ficoll-Hypaque density gradient centrifugation, will be analyzed for changes in standard immune cell types (CD4 and CD8 T cells, natural killer [NK] cells, regulatory T cells [Tregs], myeloid-derived suppressor cells [MDSCs], and dendritic cells) as well as 123 immune cell subsets, as described elsewhere (Lepone et al 2016)⁸⁰.
- 2 Analyses of soluble factors: Sera will be analyzed pre- and post-therapy for the following soluble factors: sCD27 and sCD40 ligand.
- 3 Additional assays: Blood samples may be used for additional research studies, which may include phenotypic and functional analysis of immune-cell subsets (such as CD4 and CD8 T cells, NK cells, Tregs, and MDSC), T cell clonality, circulating tumor cells, RNA and proteomic analyses, and analyses of cytokines (such as IFN- γ , IL-10, IL-12, IL-2, IL-4, etc.), chemokines, antibodies, tumor-associated antigens, and/or other markers.

c) Insulin (plasma)

Our core analyses will explore the indirect, insulin mediated, effect of metformin as a predictor of invasive disease free survival (primarily), overall survival and prostate cancer free interval, including an evaluation of both baseline fasting insulin (primarily), change in insulin over 9 weeks (secondarily) and at the end of treatment. This primary focus on insulin reflects the recognition that insulin at diagnosis is a prognostic factor in prostate cancer, and it reflects the major impact metformin has on insulin levels; our hypothesis is that higher insulin

level at baseline will predict metformin benefit in the overall study population. Additionally, in exploratory analyses we will examine the relationship between changes in insulin level during the first 6 months of metformin administration.

d) Glucose (plasma)

We plan to examine whether baseline glucose predicts metformin benefit independent of insulin or whether glucose modifies effects of insulin as a predictor of metformin benefit. We will also investigate Homeostasis Model Assessment (HOMA), an empirically derived estimate of insulin sensitivity calculated from a single measure of fasting insulin and glucose that correlates well with the gold standard frequently sampled intravenous glucose tolerance test, as a predictor of metformin benefit, focusing on whether it provides additional prediction beyond insulin alone

Research Blood Samples Taken at Baseline and Again at 9 weeks and at End of Study Treatment	One Tube (7 ml) (1.4 teaspoons)	Light Green Top Tubes (3 x 4.5 ml) (2.7 teaspoons)	Red Top Tube (2 x 6 ml) (2.4 teaspoons)	Lavender Top Tube (1 x 6 ml) (1.2 teaspoons)
	Sera for Fasting Glucose (done locally according to institution's procedures & mandatory)	Insulin (done centrally & mandatory) Plasma for storage for future research (optional)	Serum for storage for future research (optional)	DNA extraction (done centrally & optional) Lavender topped tubes for DNA should be collected even for patients who consent to blood banking but refuse genetic testing. DNA may be used to study gene expression without fitting the definition of genetic testing.

Research Blood Samples Taken at Baseline and Again at 9 weeks and at End of Study Treatment	Green Top Sodium Heparin tubes (6 x 10 ml)	SST tubes (2 x 8 ml)
--	--	----------------------

	PBMC for immune assessments (done at the NCI & mandatory)	Serum samples for soluble factor analyses (done at the NCI & mandatory)
--	--	--

TOTAL VOLUME DRAWN = 114.7 ML

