11.0 STATISTICAL CONSIDERATIONS

11.1 Sample size

We will test the hypothesis that only 20% of patients on either arm of the study will have undetectable PSA at 32 weeks, versus the alternative that 40% of arm B patients will. An initial cohort of 39 patients and, if continued, a second cohort of 27 patients will be randomized 2:1 to arms B and A respectively.

After stratification for prior therapy we will randomize, 2:1, nominally 13 patients to arm A and 26 patients to arm B. Because of post stratification randomization, the exact numbers in the two arms may vary slightly from 13 and 26, but the total patient number in the the initial cohort will be exactly 39 and the final sample number be exactly 66. Our intent is to compare the proportions of patients with undetectable PSA at 32 weeks. This is most simply described by the difference $(E1/26) - (C1/13)$, where C1 and E1 are the numbers of undetectable PSAs in arms A and B respectively. The cut point for continuation of the trial past the first cohort requires that

$(E1/26) - (C1/13) > -2/13 = -0.1538462\dots$. To avoid confusion due to round off of such fractions, we identify the decision boundary by $13 E1 - 26 C1 > -52$, exactly equivalent the first expression, and obtained by multiplying all terms by $13*26$.

If $13 E1 - 26 C1$ exceeds -52 AND $E1$ is at least 6 then we will randomize an additional 9 patients to arm A and 18 patients to arm B. Otherwise the study will be terminated and the null hypothesis accepted. Letting $C2$ and $E2$ be the numbers of undetectable PSAs in the second cohort, we will finally reject the null hypothesis if $22(E1 + E2) - 44(C1 + C2)$ is at least 88 and $E1 + E2$ is at least 14. The initial cohort will consist of 39 and the final cohort of 27 patients for a total of 66 patients. If the true null is 20% undetectable PSAs type I error will be 3.24% and power will be 80.3%. In this case the chance of early stopping under the null will be 60% but will be 3.23% if the true arm B fraction of undetectable PSAs is 40%.

If the null (arm A) fraction undetectable PSAs is 25% type I error increases to 10.9% and power increases to 83.3% if the arm B fraction undetectable is 45% (20% higher). If the null fraction is 30% type I error increases to 19.7% and power to 83.2% (arm B 50%, 20% higher).

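### Correlative analyses: markers meant to predict metformin benefit include post-randomisation values, and no arm-by-marker analysis is named for any marker

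*Combined protocol and SAP*

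**What the plan says.** Section 8.2.1 (Use of Tumor Blocks) states for the insulin receptor: "We plan to quantify IR expression by IHC and correlate results with clinical outcomes". LKB1 gets the same treatment. The signalling-pathway activation markers are to be evaluated as predictors of metformin benefit, with no method given.

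Section 8.3 b) (Use of Blood Samples) names a core group of blood variables with three sampling times, the later two in these words: "9 weeks after enrolment and at the end of treatment) and tumor related factors (at diagnosis) will be examined as predictors of metformin benefit". The baseline values belong to that same sentence.

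Section 8.3 c) makes baseline fasting insulin the main analysis, followed by "change in insulin over 9 weeks (secondarily) and at the end of treatment". It hypothesises that higher baseline insulin predicts benefit, describes insulin as prognostic in its own right, and says that metformin affects insulin strongly. Section 8.3 d) asks whether baseline glucose and HOMA predict benefit. For the genomic profile, Section 8.3 a) leaves the method open until analysis.

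Section 11 contains no biomarker analysis. Nowhere do the documents name an arm-by-marker term or a comparison of the arm B minus arm A difference across marker levels.

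**The concern.** To predict benefit from metformin is to say that the difference between arms varies with the marker. That needs both arms and a contrast between them at each marker level. Three things in the plan do not meet this.

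- **Correlation with outcome (IR, LKB1).** A marker of good prognosis correlates with outcome whether or not metformin works better in marker-positive men.
- **Post-randomisation blood values.** Arm A is untreated in cycles 1 and 2 (Section 5.3.1) while arm B takes metformin (Section 5.3.2). The week-9 value is therefore an on-metformin value in arm B only. It is partly a result of treatment, and men grouped by it are no longer compared as randomised.
- **End-of-treatment values.** For men who complete treatment, this sample is drawn at week 32 or 33 (Table 1 and Sections 6.4 and 8.3). The primary endpoint is at week 32 (Section 2.1), so the sample comes at or after the result it would predict.

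The risk is that a prognostic marker is later presented as a way of selecting men for metformin. The randomised arm A lets the question be asked properly, though with little precision.

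**Working it through.** **1. Inputs from the documents.** The null hypothesis in Section 11.1 is that "only 20% of patients on either arm of the study will have undetectable PSA at 32 weeks". Under the alternative, the arm B rate is 40%. Allocation is 2:1, with a "final cohort of 27 patients for a total of 66 patients", nominally 22 in arm A and 44 in arm B. The documents give no figure for any biomarker analysis. The only stated figures to reproduce are those of the two-stage design. Exact binomial enumeration (continue if 13·E1 − 26·C1 > −52 and E1 ≥ 6; reject if 22·E − 44·C ≥ 88 and E ≥ 14) gives:

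| | Stated | Recomputed |
|---|---|---|
| Type I error | 3.24% | 3.246% |
| Power | 80.3% | 80.36% |
| Early stopping, null | 60% | 60.05% |
| Early stopping, alternative | 3.23% | 3.236% |

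The small differences are truncation.

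**2. Why correlation does not answer the question.** Assume a purely prognostic marker that splits the men in half: arm A 35% and 5% undetectable, with metformin adding 20 points in both halves (arm B 55% and 25%). Nobody benefits more than anyone else.

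- Arm B alone, 22 per half: SE = √(0.55·0.45/22 + 0.25·0.75/22) = 0.141. Then z = 0.30/0.141 = 2.13, and the chance of p < 0.05 is about 57%. Simulation of 4,000 trials gave 56%.
- Both arms pooled with adjustment for arm: 78% in simulation.
- Arm-by-marker interaction: 6% in simulation, close to the nominal 5%.

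**3. How far metformin shifts a change-based grouping.** The documents give no insulin effect, SD or cut-point. Assume that metformin lowers insulin by 25%, arm A is unchanged, the SD of log change is 0.3 to 0.5, and men whose insulin falls by more than 15% are grouped together.

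- SD 0.3: arm B Φ((ln 0.85 − ln 0.75)/0.3) = 66%; arm A Φ(ln 0.85/0.3) = 29%. The arm B share of this group is 2·0.66/(2·0.66 + 0.29) = 82%, and of the rest 49%.
- SD 0.5: 60% and 37%. The arm B share is 76%, and of the rest 56%.

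The allocation alone gives 67% arm B in each group, so the imbalance is 9 to 15 points above that.

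**4. Precision of the proper analysis.**

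- Main effect: SE = √(0.20·0.80/22 + 0.40·0.60/44) = √0.01273 = 0.113.
- Interaction, equal halves: SE = √(2·(0.16/11 + 0.24/22)) = 0.226, twice the main-effect value.

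Power at two-sided 5%, assuming arm A at 20% in both halves and complete marker data:

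| Arm B, marker-negative and marker-positive | SE | Power, N = 66 | N for 80% |
|---|---|---|---|
| 20% and 60% | 0.217 | 45% | 154 |
| 25% and 55% | 0.221 | 27% | 282 |
| 30% and 50% | 0.224 | 15% | 648 |

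In the first row, power falls to 30% if tissue is available for only 60% of men (Section 8.2 makes it optional), and to 29% if the trial stops at 39. Power is high (86%) only in an extreme case: 30% of men marker-positive, with the whole effect in them (20% against 87% in arm B).

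**The case against.** The strongest reply is that most of this is unspecified rather than wrong. That is partly right. Correlation is the stated method only for IR and LKB1. For the pathway markers, insulin, glucose and HOMA no method is given, and for genomics it is openly deferred. Section 8.3 itself distinguishes prognostic from predictive factors. The lead insulin and glucose hypotheses use baseline values, which both randomised arms can test validly. Serial insulin also has a proper mechanistic purpose, stated at the start of Section 8.3: to explore whether metformin acts through insulin. What remains is that the sentence in Section 8.3 b) puts later values among the predictors of benefit, and that no stated method answers the predictive question.

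A reader might infer two stronger criticisms that the documents do not support.

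- **Guarantee-time bias.** Section 7.3 says "Survival will be measured from the date of randomization", so it is tempting to argue that men must remain event-free to give the later samples. But Section 7.4 counts PSA progression only after bicalutamide starts, which is not before cycle 3, so almost no countable event can precede the week-9 sample. Section 6.4 also takes research blood from men who stop early. Section 1.1 puts median survival from biochemical recurrence at around 13 years, so early deaths would be very few. The primary endpoint is a fixed-time proportion.
- **Grouping by insulin change mostly recreates the arms.** Under the assumptions in step 3, 76–82% arm B against an expected 67% is an imbalance, but 29–37% of arm A falls in the same group. In simulation, a change shifted 1 SD by metformin but with no role in outcome reached p < 0.05 in 13% of pooled analyses. That is above 5%, but not a near-replacement of the arm comparison.

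It can also be said that at 66 men the answer will be weak whatever is done. That is true, and it argues for an interval and an exploratory label, not for an analysis of a different question.

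**Conclusion.** The point holds for the correlative analyses only. As written, they cannot distinguish a predictive from a prognostic marker for IR and LKB1, they name values altered by metformin as predictors of its benefit, and they include a sample taken at or after the week-32 endpoint. For the remaining baseline and diagnostic markers the defect is a missing analysis, not a wrong one. The primary comparison and its error rates are untouched. These tissue and metabolic markers are not listed among the endpoints in Section 2.

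The firm part rests on the text alone. The size rests on assumptions: a median-split marker, complete data, the planning rates of 20% and 40%, and a final 22 and 44 men. On these the interaction standard error is about 0.23 against 0.113, and power is about 15% to 45% in the scenarios shown for a median-split marker. Any finding would be hypothesis-generating. The change should be made because it costs little and prevents a misleading claim.

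**What to change.** - Restrict the term predictor of metformin benefit to markers fixed before treatment: IR, LKB1, the pathway markers, baseline insulin, baseline glucose and baseline HOMA.
- For each, fit outcome on arm, marker and arm-by-marker using both arms, adjusted for the prior-therapy stratum used in randomisation. Report the interaction with its confidence interval, labelled hypothesis-generating. State this in Section 11 and refer to it from Sections 8.2.1 and 8.3.
- Analyse week-9 and later insulin changes as effects of metformin, by comparing arms, or as mechanistic analyses described as such.
- Drop end-of-treatment values as predictors of the week-32 result.

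The cost is analysis text only: the samples and visits stay the same. The downside is wider intervals than a simple correlation would give.
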